8.2. Number of Patients

Up to 600 patients are planned for screening. This is expected to result in a final sample size of up to 540 eligible and evaluable enrolled patients, distributed among approximately 50 investigative sites in the US.

Table 3: Schedule of Assessments

Protocol Activity (Visit Type, Location, and Number; Study Day and Month; Window Allowance)	2-Month Main Study			4-Month Extension Study		
	Screening/Baseline Assessment Visit ^a	Follow-up	Primary Endpoint Visit	Follow-up	PRO Assessment Only	Follow-up
	Clinic	Telephone	Clinic	Clinic		Clinic
	Visit 1	Visit 2	Visit 3	Visit 4	Visit 5	Visit 6
	Day 1	Day 30	Day 60	Day 90	Day 120	Day 180
	Month 1		Month 2	Month 3	Month 4	Month 6
	±7 days	±2 days	±7 days	±7 days	±7 days	±14days
Informed Consent and HIPAA Authorization	X					
Eligibility: Inclusion/Exclusion Criteria	X					
Medical History and Demographics	X					
Medical History of PD, other Neurological Conditions	X					
Presentation of Study Instructions to Patient	X					
Registration and Training on eCOA System	X					
Concomitant Medications Assessment ^b	X	X	X	X		X
XADAGO Administration Compliance Review ^b		X	X	X		X
PRO Compliance Review ^b			X	X		X
Adverse Events Assessment ^b			X	X		X
MDS-UPDRS ^b	X		X	X		X
PDQ-39 ^c	X		X	X		X
MoCA ^b	X		X			X
TSQM-9 ^c		X	X	X	X	X
CGI-C ^b			X	X		X
PGI-C ^c			X	X		X

^a Screening will take place not more than 7 days before the Baseline Visit and may occur at the same time as the Baseline Visit. The first study dose of XADAGO will occur in the clinic on the Baseline Visit day, which will be designated Study Day 1.

^b Assessments to be administered by the PI/certified or HCP designee.

^c Assessments to be completed by the patient, with Care Partner assistance, if required.

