12. STATISTICAL METHODS

12.1. General Statistical Considerations

All assessments will be summarized at specified time points. Continuous variables will be summarized using the number of patients, mean, standard deviation (SD), and minimum, median, and maximum values. Categorical variables will be summarized using the number and percentage. All data will be summarized according to cohort and overall.

Endpoints are defined at Study Day 60 (primary endpoint). Descriptive statistics will be provided for all data collected. All tests of significance, unless otherwise stated, will be performed using a two-sided alpha at 0.05.

All analyses will be performed using SAS[®] Version 9.3 or higher (SAS Institute, Inc., Cary, North Carolina, USA).

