12.3. Sample Size and Decision Rules

This is an observational study that will not assign treatment to patients. Patients will be analyzed collectively and in one of 3 cohorts based on the study entry criteria. A sample size of up to 540 patients was selected to ensure a meaningful representation in each of the 3 cohorts.

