### **4.3. Sample Size Considerations**

#### **4.3.1. Sample Size Justifications**

Since this is an observational study, sample size is determined based on clinical judgment. Up to 600 patients are planned for screening. This is expected to result in a final sample size of up to 540 eligible and evaluable enrolled patients, distributed among approximately 30 investigative sites in the US.

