## **6.4. Data Presentation Conventions**

Continuous variables (e.g. age) are summarized using descriptive statistics (the number of subjects with available data, the mean, standard deviation (SD), median and minimum and maximum). Categorical variables (e.g. race) are summarized using counts and percentages. Percentages are calculated using the total subjects in the XADAGO group.

The following conventions are applied to all data presentations and summaries.

- For continuous variables, all mean and median values are formatted to one more decimal place than the measured value. Standard deviation values are formatted to two more decimal places than the measured value. Minimum and maximum values are presented with the same number of decimal places as the measured value.
- For categorical variables, the number and percentage of responses are presented in the form XX (XX.X%) where the percentage is in the parentheses.
- Date variables are formatted as DDMMYY for presentation. Time is formatted in military time as HH:MM for presentation.
- Wherever possible, data will be decimal aligned.
- Unless otherwise stated, any statistical tests performed will use 2-sided tests at the 5% significance level.

The table and listing shells and table of contents as part of this SAP provide the expected layout and titles of the tables, listings and figures. Any changes to format, layout, titles, numbering, or any other minor deviation will not necessitate a revision to the SAP nor will it be considered a deviation from planned analyses. Only true differences in the analysis methods or data handling will necessitate such documentation. The appropriate listings supporting the tables will be included and are not specified in the individual sections throughout the document.

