### **8.4. Analysis of the Efficacy Endpoint**

The change in MDS-UPDRS, PDQ-39, and MoCA from the Baseline Assessment Visit to the Primary Endpoint (Study Day 60) will be summarized by cohort and overall. An analysis of paired t-test will be used to analyze the continuous endpoints.

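### If changes correlate within site, the plain paired t-test in SAP 8.4 understates the standard error and exceeds its 5% level

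*SAP*

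**What the plan says.** SAP 8.4 gives one inferential method for the primary outcome: "An analysis of paired t-test will be used to analyze the continuous endpoints". The results "will be summarized by cohort and overall". The level is the same in both documents: in SAP 6.4, "any statistical tests performed will use 2-sided tests at the 5% significance level"; in Protocol 12.1, tests "will be performed using a two-sided alpha at 0.05".

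Site is used for population counts (Protocol 12.7), disposition (SAP 7.1) and the sorting of listings (SAP 6.1). It has no place in the outcome analysis. The covariates in Protocol 12.5 are age, sex and disease duration.

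The number of sites is given twice and differs. Protocol 8.2 has patients "distributed among approximately 50 investigative sites in the US", and the protocol synopsis agrees. SAP 4.3.1 has them "distributed among approximately 30 investigative sites in the US".

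The sample size has no effect size, SD or power behind it. Protocol 12.3 says "A sample size of up to 540 patients was selected to ensure a meaningful representation in each of the 3 cohorts", and SAP 4.3.1 says "sample size is determined based on clinical judgment".

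**The concern.** A paired t-test handles the pairing of two visits within a patient. It does not handle likeness between patients of the same site. In a single-arm study, any site-level component of the change goes into the variance of the overall mean, with no second arm to cancel it.

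The documents leave several routes by which changes could be alike within a site:

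- The investigator or a designee may rate (Protocol 8.1.1 and 8.1.3), and nothing requires the same rater at baseline and Day 60.
- Protocol 8.1.1 asks that patients arrive in an on state at baseline. Protocol 8.1.3 does not repeat this for Day 60, so the motor state at that visit may follow site habit.
- XADAGO and other PD medication are taken as the treating physician directs (Protocol 10.1.3.2 and 10.2), so local dosing and concomitant-medication practice can act on the change itself.
- Raters know that every patient was prescribed XADAGO, so a site's expectations can shift its ratings.

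The rater routes apply to MDS-UPDRS Parts IA, III and IV and to MoCA. PDQ-39 and MDS-UPDRS Parts IB and II are completed by the patient (Protocol 7.2.1 and 7.2.2), so for these only local practice applies.

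At stake is the precision claimed for the mean changes. Protocol 12.6 foresees posters and publications, including of interim results.

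**Working it through.** **Inputs from the documents.** Two-sided alpha 0.05 (SAP 6.4, Protocol 12.1). N = 540, the stated maximum. Sites: 50 (Protocol 8.2) or 30 (SAP 4.3.1).

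**Assumed inputs.** The ICC of the change score within site is not in the documents; values from 0 to 0.05 are shown. Sites are of equal size unless noted. For the cohorts, an equal split of 540/3 = 180 is assumed, because no split is stated.

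**The plan's own figures.** The 540 cannot be reproduced, because no effect size, SD or power is given. The 5% level can: with ICC = 0 the paired t-test holds it, and simulation (20,000 runs per setting) gave 4.8% to 5.1%.

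**Formulas.**
- Patients per site: m = N / sites, so 540/50 = 10.8 and 540/30 = 18.
- Design effect: DE = 1 + (m − 1) × ICC.
- Ratio of true to nominal standard error: r = √(DE / (1 − (DE − 1)/(N − 1))). The denominator allows for the sample SD also being slightly affected.
- True level = 2 × (1 − Φ(1.96 / r)).

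**One case in full (30 sites, ICC 0.05).** DE = 1 + 17 × 0.05 = 1.85. r = √(1.85 / (1 − 0.85/539)) = 1.361. 1.96/1.361 = 1.44, so the level is 15.0%.

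**Overall test, N = 540.**

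| ICC | 50 sites: DE | r | level | 30 sites: DE | r | level |
|---|---|---|---|---|---|---|
| 0 | 1.00 | 1.00 | 5.0% | 1.00 | 1.00 | 5.0% |
| 0.01 | 1.098 | 1.048 | 6.1% | 1.17 | 1.082 | 7.0% |
| 0.02 | 1.196 | 1.094 | 7.3% | 1.34 | 1.158 | 9.1% |
| 0.05 | 1.49 | 1.221 | 10.9% | 1.85 | 1.361 | 15.0% |

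At ICC 0.05 the effective number of patients is 540/1.49 = 362 (50 sites) or 540/1.85 = 292 (30 sites). Simulation at that ICC gave 11.1% and 14.7% with equal sites. With unequal sites (coefficient of variation of size about 0.7) it gave about 15% and 20%.

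**One cohort, assumed 180 patients, ICC 0.05.** With 50 sites m = 3.6, DE = 1 + 2.6 × 0.05 = 1.13, r = 1.063, level 6.5%. With 30 sites m = 6, DE = 1 + 5 × 0.05 = 1.25, r = 1.119, level 8.0%.

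**After the change.** With a site-clustered standard error and t on (sites − 1) degrees of freedom, at N = 540 and ICC from 0 to 0.10, the simulated level was 4.8% to 5.3% with equal sites and 5.2% to 6.2% with unequal sites.

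**The case against.** A reader might infer that the standard errors are certainly too small and the 5% level is certainly missed. The documents do not support that. Both depend on an ICC that is not given; at 0 the level is exact, and at 0.01 it is 6.1% or 7.0%.

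A reader might also infer that differences in rater severity alone cause the problem. They do not. The endpoint is within-patient change (SAP 6.7.3), so a stable tendency to score high or low is in both visits and cancels. Only site differences in change count. That weakens the case for a large ICC without removing it, for the reasons given under the concern.

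If the enrolled sites were the whole population of interest, the plain test would be slightly conservative: in simulation with 30 fixed sites the level was 4.5% at ICC 0.05 and 4.0% at 0.10. Neither document addresses this choice directly. However, the objective in Protocol 7.1 and SAP 3.1 is about people with Parkinson's disease in the US, which makes the sites a sample.

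Three further points stand. The 15.0% combines the maximum N, the smaller site count and the highest ICC in the table, and it is for the overall test only. No confidence interval is planned, so the only planned output at risk is the p-value and the standard error behind it. And the study is observational, with no success rule tied to a p-value.

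**Conclusion.** The point holds in conditional form. The planned test ignores site, and for the stated US target any positive within-site correlation of change makes its standard error too small. Over the assumed ICCs of 0.01 to 0.05, the overall 5% level becomes about 6% to 11% with 50 sites and 7% to 15% with 30. It is closer to nominal by cohort, and higher for the overall test if site sizes are unequal. These figures rest on the assumed ICC, the full 540 patients and equal sites.

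The consequence is overstated precision in reported results, not a wrong trial decision. The change is still worth making because the t-test is the only inference planned for the primary outcome and the remedy is cheap. The two site counts are a plain contradiction that needs correcting in any case, but the contradiction does not by itself show an analysis error.

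**What to change.** In SAP 8.4, keep the mean change as the estimate. Take its standard error and p-value, and a confidence interval if one is reported, from a site-clustered robust variance with t on (sites − 1) degrees of freedom, overall and by cohort. A random site intercept is not a substitute: with unequal sites it re-weights the mean, so its standard error does not belong to the plain mean change.

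The cost is one SAP sentence and a few lines of code. Error bars widen if the ICC is positive (by a factor of 1.22 with 50 sites or 1.36 with 30 at ICC 0.05) and hardly change if it is near zero.

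Separately, reconcile the number of sites between Protocol 8.2 and SAP 4.3.1.

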## **9. SAFETY AND TOLERABILITY**

The analysis of safety and tolerability data includes an overall summary of tolerability, adverse event preferred terms by body/organ system, drug exposure (duration of treatment) by treatment (50 mg vs 100 mg), dosing information/compliance, concomitant medications, clinical laboratory results, vital signs, physical examination, and study termination status. Tables summarizing the adverse events reported by subjects who died, experienced non-fatal serious adverse events (SAE), or prematurely discontinued the study due to adverse event (AEs) will be prepared. Summaries of potentially clinically notable laboratory results and vital sign abnormalities will be presented. Paired subject data listings will be provided to support the summaries of SAEs and these will be sorted first by subject and then by event preferred term or parameter.

### **9.1. Overall Summary of Tolerability**

The overall summary of tolerability table presents the data for all treated subjects by cohort and overall. Entries in this table are the number of:

1. Subjects treated and subject months of drug exposure by treatment (50 mg vs 100 mg).
2. Subjects with adverse events.
3. Adverse events.
4. Subjects with serious adverse events.
5. Subjects discontinuing due to adverse events.
6. Deaths.

The subject data listing provides a complete disclosure of adverse events as recorded in the CRF and supports this table and all other AE summary table subsets.

### **9.2. Adverse Event Preferred Term and Body/Organ System Summary Tables**

AEs will be presented according to a treatment emergent signs and symptoms algorithm. These events are first observed after the initiation of study drug and are captured until the follow-up visit. Adverse events will be counted if they occur no more than 2 days after the cessation of treatment for non-serious events and within 30 days following the cessation of treatment for serious events.

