10.1.4. XADAGO Discontinuation

If an enrolled patient discontinues XADAGO treatment for any reason at any point in the study, the patient is permitted to remain on study and complete the full schedule of assessments per protocol, as long as the patient is otherwise eligible, and is able and willing to continue study participation through the end of the Main Study or the Extension Study, as appropriate. Refer to Section 9.4 for patients who discontinue XADAGO and wish to discontinue the study.

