11.4. Recording Adverse Events

AEs spontaneously reported by the patient and/or in response to an open question from the study personnel or revealed by observation will be recorded during the study at the investigational site.

Information about AEs (and SAEs) will be collected from the time the patient signs the informed consent for this study and takes the first study dose of XADAGO until the patient’s last follow-up visit. The AE term should be reported in standard medical terminology when possible. For each AE, the investigator will evaluate and report the onset date, resolution date, intensity, causality, action taken, serious outcome (if applicable), and whether or not it caused the patient to discontinue the study.

Intensity will be assessed according to the following scale:

- Mild (awareness of sign or symptom, but easily tolerated)
- Moderate (discomfort sufficient to cause interference with normal activities)
- Severe (incapacitating, with inability to perform normal activities)

It is important to distinguish between serious and severe AEs. Severity is a measure of intensity whereas seriousness is defined by the criteria under Section 11.2.2. An AE of severe intensity may not be considered serious.

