11.4.2. Serious Adverse Event (SAE)

All SAEs (related and unrelated) that occur for any patient after signing an informed consent for this study and having taken XADAGO must be recorded by the investigator and reported. The site should record the SAE in the patient's source medical record within 24 hours of observation or notification that such an event has occurred. The patient's medical record should be completed with as much information as is available at that time with the knowledge that full clinical details may not be immediately available. The Sponsor will contact the site if additional information is required regarding the SAE. In addition, an SAE form located in the ISF binder must be completed and submitted to (see [Table 1](#) for details).

All SAEs must be followed until they resolve or stabilize (i.e., a new baseline has been established). The PI must provide the Sponsor with all relevant follow-up information necessary to facilitate a thorough understanding of the experience and judgment regarding the relationship to XADAGO. Patients who discontinue because of an SAE before study completion will be contacted 7 days (± 3 days) after discontinuation to determine if the SAE has resolved, continues unabated, or has reached a new baseline.

Reports of congenital abnormalities/birth defects are SAEs. Spontaneous miscarriages should also be reported and handled as SAEs. Elective abortions without complications should not be handled as AEs.

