12.9.2. Safety Analysis

Serious and non-serious AEs will be collected as part of this study and reported for each cohort and overall.

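### The SAP 9.2 adverse event tables leave out events that the protocol collects and says it will report in patients who stop XADAGO but stay in the study: non-serious AEs starting more than 2 days after stopping, and SAEs starting more than 30 days after

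*SAP*

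**What the plan says.** SAP 9.2 presents AEs under a treatment-emergent algorithm. Events first seen after XADAGO starts "are captured until the follow-up visit". The next sentence narrows what is counted: "Adverse events will be counted if they occur no more than 2 days after the cessation of treatment for non-serious events", and serious events only "within 30 days following the cessation of treatment for serious events". SAP 9.1 describes a tolerability table for all treated subjects with no window stated, supported by a listing of every AE recorded in the CRF.

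The protocol sets a different period. Under 11.4, information on AEs and SAEs is collected from consent and first dose "until the patient’s last follow-up visit". Under 10.1.4, if XADAGO is discontinued, "the patient is permitted to remain on study and complete the full schedule of assessments per protocol", through the end of the Main or Extension Study. The Schedule of Assessments places AE assessments at Days 60, 90 and 180. Protocol 12.9.2 commits as follows: "Serious and non-serious AEs will be collected as part of this study and reported for each cohort and overall". It mentions no limit relative to stopping.

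On follow-up after leaving the study, Protocol 11.4.2 says: "Patients who discontinue because of an SAE before study completion will be contacted 7 days" (±3) after discontinuation, to check the status of that SAE. Sections 9.4 and 11.4.2 also require SAEs to be followed until they resolve or stabilise; 9.4 extends this to intolerable AEs that lead to removal.

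**The concern.** The protocol deliberately keeps patients under observation after they stop the drug, and its AE definition covers conditions arising during or following exposure. The SAP then discards part of that observation from the summary tables. Neither the 2-day nor the 30-day limit appears in the protocol, and the SAP gives no reason for either.

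The omission goes in one direction: it can lower the tabulated incidence of AEs and SAEs but never raise it. A reader who takes Protocol 12.9.2 at its word would assume that the tables cover everything collected. No planned table shows events starting after the window, so that reader would have to rebuild the count from the listing.

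A second mismatch concerns patients who leave the study when XADAGO stops. Their collection ends at the last visit, and the protocol schedules no 30-day enquiry about new SAEs. For them the 30-day limit omits nothing, but it has no matching data collection behind it.

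**Working it through.** The plan states no figure on this point, so there is none to reproduce. The check is day arithmetic.

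**Inputs**
- Counting limits after stopping: 2 days (non-serious) and 30 days (serious), SAP 9.2.
- Last visit E: Day 60 (Main Study) or Day 180 (Extension), at nominal dates without the visit windows.
- Stop day s: day of last dose. The documents give no distribution, so s = 20 is an example.
- The limits are read as applying to the day on which the event starts.

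**Formulas**
- Days observed after stopping: E − s
- Uncounted days, non-serious: max(0, E − s − 2)
- Uncounted days, serious: max(0, E − s − 30)

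**Stop on Day 20**

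| Patient stays to | Observed after stopping | Non-serious AEs uncounted | SAEs uncounted |
|---|---|---|---|
| Day 60 | 60 − 20 = 40 | 60 − 22 = 38 (Days 23–60) | 60 − 50 = 10 (Days 51–60) |
| Day 180 | 180 − 20 = 160 | 180 − 22 = 158 (Days 23–180) | 180 − 50 = 130 (Days 51–180) |

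**Other stop days**
- Stop Day 14, stay to Day 60: 44 of 46 days uncounted for non-serious AEs, 16 of 46 for SAEs.
- Stop Day 30, stay to Day 60: 28 of 30 and 0 of 30.
- Stop Day 60, stay to Day 180: 118 of 120 and 90 of 120.

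**When a gap exists.** With a last visit on Day 60, any last dose up to Day 57 leaves uncounted days for non-serious AEs, and any up to Day 29 does so for SAEs. With a last visit on Day 180, the corresponding days are 177 and 149.

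**How many patients.** The documents do not say how many will stop and stay. If it were 5% to 20% of 540 (an assumption), that would be 540 × 0.05 = 27 to 540 × 0.20 = 108 patients with uncounted time. This is a count of patients at risk of an omission, not of omitted events.

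**After the fix.** If counting runs to the last study contact, uncounted days are 0 for both classes.

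**The case against.** The best defence is that a treatment-emergent window is a recognised convention, that late events off drug are often unrelated to it, that safety is not the principal objective here (Protocol 11.1), and that the listing discloses every recorded AE. Most of this stands. It justifies keeping an on-treatment view and rules out any suggestion that events are hidden. It does not reconcile the SAP with Protocol 12.9.2, which sets no cut-off, and a listing is not a summary by cohort and overall.

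Some stronger readings are tempting, but the documents do not support them:

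- **That the events which made patients stop are lost.** An AE that leads to stopping starts before stopping, so it is counted. SAP 9.1 and 9.2.3 also tabulate discontinuations due to AEs. Only new events starting after the window are lost.
- **That every AE table is affected.** The rule sits in 9.2, and the 9.1 table states no window. Whether it applies there is unclear.
- **That most of the 30 days goes unobserved after a patient leaves because of an SAE.** The call at 7 (±3) days is not the end of contact, because existing SAEs are followed until they resolve or stabilise. What is missing is scheduled enquiry about new SAEs.
- **That the plan counts off-drug benefit but not off-drug harm.** Off-drug Day 60 scores do enter the analysis, but they may show worsening as well as improvement.
- **That 2 days is too short pharmacologically.** The Package Insert is an appendix whose text is not available here, so this cannot be judged. The point does not need it.

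**Conclusion.** The conflict is real and can be shown from the two documents alone. Following SAP 9.2 as written leaves collected events out of the AE tables for patients who stop XADAGO and remain in the study: nearly all of their off-drug time for non-serious AEs, and everything beyond 30 days for SAEs.

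The conclusion rests on reading the limits as applying to event onset and the stop date as the last dose. The day counts are examples at nominal visit dates. The effect on incidence cannot be sized, because neither the number of patients who stop and stay nor their event rate is given. The Day 180 figures also need Extension data to be in the database; SAP 5.2 locks it after the last subject's Visit 3, so some of that follow-up may come later. Patients still on XADAGO at their last visit lose nothing.

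This should be corrected before the tables are produced, but it does not undermine the study's main analyses.

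**What to change.** In SAP 9.2:

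1. Tabulate all AEs and SAEs with onset from first dose to the patient's last study contact, by cohort and overall.
2. Split these into on-treatment and after-stopping using the XADAGO stop date. The existing 2-day and 30-day limits may be kept as the definition of on-treatment.
3. State that the same rule governs the counts in SAP 9.1.
4. Describe the SAE follow-up that exists after stopping: collection to the last visit for those who stay; for those who leave, follow-up of existing SAEs, with no scheduled 30-day enquiry about new ones.

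The split depends on onset dates. SAP 9.2.2 sends missing or partial dates to Section 6.8.1, which covers only carrying forward efficacy values, so a date rule should be written at the same time.

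The cost is SAP wording and one extra split in the AE tables, with no new data. Reported incidence may rise, and some late events will be unrelated to XADAGO; the split lets the reader see which events those could be.
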